Other studies have emulated the benefit of pre-operative radiation therapy. A Meta-Analysis reviewed 5 studies in which 1098 patients with localized and resectable STS were treated with either pre- or post-operative radiation therapy. In this study, local control and survival was improved in the pre-operative RT group (HR 0.6, SS) and 76% versus 67%. These results have also been shown in other studies (6).

Although pre-operative RT has been shown to compare favorably with post-operative RT, there are certain disadvantages. Acute wound complication rates are higher when radiation is administered in a pre-operative manner. In the NCI Canadian randomized control trial, the major acute wound complication rate was 35% versus 17% in patients who received post-operative radiation therapy. Moreover, a higher percentage of patients in the pre-operative cohort required non-primary wound closure and had poorer 6-week post-operative function. Increasing wound complications when RT is administered pre-operatively has been consistently seen in other studies and ranges from 25-35% (5). However, long term functioning and toxicity is improved with pre-operative radiation therapy (7).

As an extrapolation of the NCI protocol, late radiation morbidity was evaluated in patients who participated in this trial. In this study, post-operative RT was associated with worse fibrosis and joint stiffness compared to preoperative RT. In the post-operative treatment arm, 48% of patients developed grade 2 or higher fibrosis compared to 31% in the pre-operative arm ($p=0.07$). Moreover, edema was also higher in the post-operative radiation arm (7).

Because of the above studies, there has been a transition of treatment with pre-operative radiation therapy. This consists of daily radiation (Monday through Friday) over a course of 5 weeks (25 treatments). Pre-operative radiation is followed by surgical resection 4-8 weeks later.

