While the approach of radiation, surgery, and chemotherapy has good outcomes in terms of toxicity and local control, there is always room to improve these treatments. The NCI of Canada SR2 trial had a wound complication rate of 43% and studies with more modern radiation techniques such as intensity modulated radiation therapy (IMRT) continue to have wound complication rates of 30.5% (8). One possible source for improving outcome for resectable STS is to use hypofractionated radiotherapy instead of conventional radiation. Hypofractionated radiation uses a small number of radiation treatments with a high dose per fraction. Due to improved imaging and immobilization techniques the treatment is more conformal with less normal tissue receiving radiation.

Hypofractionated radiation has been used successfully in other disease sites (9-14). Perhaps the most cited literature is in early stage breast cancer. Whelan, *et al.* randomized 1234 patients with T1-2N0 invasive breast cancer to a standard course of radiation for 25 treatments over 5 weeks versus a shortened course over 3 weeks for 16 treatments. In this study, there were no differences between the control and hypofractionated groups in overall survival (84.4% versus 84.5%, respectively) or local-recurrence (6.7 versus 6.2%, respectively). Moreover, there was no difference in cosmetic outcomes and toxicity, where 71.3% of subjects in the standard radiation group compared with 69.8% of the subjects in the hypofractionated-radiation group had good or excellent cosmesis (9).

Hypofractionated radiation therapy has also been investigated in prostate cancer patients. Arcangeli, *et al.* prospectively examined 168 patients with high risk prostate cancer and randomized this subset to conventional radiation to a total dose of 80 Gy at 2 Gy per fraction versus 62 Gy at 3.1 Gy per fraction. In this study, there was a higher 3-year freedom from biochemical failure in the hypofractionated group (87%) compared to the conventional fractionated group (79%), $p=0.03$. Moreover, there was no difference in late GU (14% versus 11%, respectively) or GI (17% versus 16%, respectively) toxicity between both groups (10).

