Hypofractionation has also been used in STS study and has been shown to have favorable outcomes (11). Kosela-Paterczyk, *et al.* prospectively studied 272 patients with stage I-III STS of the extremity or trunk wall to 5 Gy x 5 fractions (25 Gy total) daily. 3-year overall survival was 72% and local control was 80%. Factors that impacted survival were STS > 10 cm and grade 3 disease. Forty-two percent of patients had some form of toxicity in this study, with the majority being the expected acute erythema and desquamation observed with RT. Seven percent of patients needed surgery to address these toxicities, which included procedures for wound healing (debridement) and wound closure. Late toxicities occurred in 15% of patients and were mainly associated with limb edema and fibrosis. Another prospective study, Kubciek, *et al.*, assessed 12 STS of the extremity that were treated to 35 Gy in 5 fractions using stereotactic body radiation techniques. Median tumor size was 7.6 cm. In this study, the local control rate was 100% and the distant metastasis rate was 42%. Most patients had some form of erythema, dry or moist desquamation which resolved within 4 weeks after the completion of radiation. There were no wound complications or late toxicity (12).

Although there are studies demonstrating the feasibility of hypofractionated radiation therapy in STS, these studies do not correlate clinical outcomes with pathologic or radiologic changes seen after radiation has completed. Association of radiologic and pathologic impact from the treatment for STS is integral as it correlates to disease control in this setting. Thus, investigating these alterations on imaging and final pathology will provide a more complete understanding of the effects of hypofractionated radiation therapy in STS.

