- i. Treatment interruptions should be minimized. More than a 2-week interruption (holidays and weekend are not included) will be considered a major violation.
- ii. Long term adverse effects will be measured 4 months after radiation for years 1 and 2

Table 3: Compliance Criteria

Per Protocol	90% of the PTV is covered with that prescription dose. No more than 10% of the PTV receives a dose that is >110% of the prescribed dose.
Minor Deviation	Greater than 10%, but no more than 20% of PTV receives ≥ 110% prescription dose. Exceeding normal tissue tolerances by >2.5%
Major Deviation	The minimum dose to any volume falls below 90% of the prescribed dose. Or, more than 20% of PTV receives ≥ 110% prescription dose. Dose to the normal tissue structure(s) is > 5%

H. Adverse Events

- i. PLACEMENT OF FLAP: Flap reconstruction and/or placement at the time of resection or soon after resection within 1 month does not constitute as a graded toxicity, as these surgeries are done to close the primary wound. Flaps are often needed as STS are large and the tissue defect caused by surgery is not able to be primarily closed. In this setting, this does not constitute as a wound complication as the flap is used for closure. Should a flap need to be placed because of a wound complication after primary resection and final closure (either primarily or with a flap), then this would constitute as a CTC AE v 4.0 Grade 4 toxicity.
- ii. Acute: Wound complications are expected to develop in about 30-40% of patients. Other common radiation adverse events include if applicable to site of lesion: fatigue, regional alopecia, diarrhea, skin erythema and desquamation within the treatment fields, and reduction in blood counts.

- iii. Long-term: Common long-term treatment adverse events include: lymphedema of the extremity receiving radiation and surgery, subcutaneous fibrosis, and joint stiffness. Much less common radiation adverse events include osteoradionecrosis and bony fracture in the radiation field. There also is a risk of cancer occurring in a previously irradiated field.
- iv. All AE's grade 3, 4 or 5 will be collected. AE's that are grade 1 or 2 will not be collected. AE's will be captured for up to 2 years post treatment, death, or initiation of a new therapy, whichever occurs first. Planned flaps are not considered an adverse event.
- v. Table 5: Criteria for Early Closure or Dose Modification.

Grade 4 Toxicity (per CTCAEv4.0)	

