4. Place cryovials into biohazard bag and immediately freeze at -70 to -90°C.
5. Store frozen plasma until ready for testing.

IX. **Assessment of Safety, Dose Modifications and Dose Delays**

- A. This study will be reviewed by the Medical College of Wisconsin Cancer Center Data Safety Monitoring Committee (MCW CC DSMC). A summary of the MCW CC DSMC activities are as follows:
 - i. Review the clinical trial for data integrity and safety.

- ii. Review all unexpected grade 3, and all grade 4, and 5 adverse events, as well as any others requiring expedited reporting as defined in this protocol. (Grades 4 & 5 events must be reported to the DSMC within 5 calendar days of study staff's knowledge.) Review all DSM reports.
- iii. Sequential boundaries will be used to monitor the post-operative wound-complication rate. The accrual will be halted if excessive numbers of grade 3 or 4 (page 32) complications are seen, that is, if the number of complications is equal to or exceeds X out of N patients (X/N) with full follow-up (see below). This is a Pocock-type stopping boundary (Ivanova, et al. 2013) that yields the probability of crossing the boundary at most 5% when the complications rate is equal to 50% (O'Sullivan, et al. 2002).
- iv. Accrual will halt for protocol review if 6/6 (6 patients out of the first 6), then 7/7, 8/8, 9/10, 10/11, 11/13, 12/14, 13/16, 14/18, 15/19, 16/21, 17/22, 18/24, 19/26, 20/27, 21/29, 22/31, 23/32, 24/34, and 25/35 grade 3-4 treatment related AE's.
- v. Submit a summary of any recommendations related to study conduct.
- vi. Terminate the study if deemed unsafe for patients.
- B. A copy of the MCW Cancer Center Data and Safety Monitoring Plan and membership roster will be maintained in the study research file and updated as membership changes.
- C. The committee will review reports from the study PI twice annually (or more frequently if needed) and provide recommendations on trial continuation, suspension or termination as necessary.

X. **Subject Withdrawal Criteria**

- A. This Protocol is designed for 35 patients. Accrual will terminate early based on toxicity analysis. Patients may also withdraw at any point if they wish to not be on study.
- B. Criteria for early Closure

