- A. The primary aim of a 2-year local recurrence rate of less than 3% will be evaluated by a one-sided equivalence test with an equivalence limit of 5% and a type I error rate of 10%. The study will conclude equivalence if the 2-year cumulative incidence of recurrence is less than 12% at the 0.10 type I error level. Power calculations are based on exact binomial probability calculations with an equivalence determined by no more than 12% local recurrence rate (within 5% of 7%), assuming a true 2-year local recurrence rate of 2.5%.
- B. If the true local recurrence rate is 12%, then with 35 patients the probability of observing a recurrence rate of 3.1% or less (≤ 1 of 35) is 8.97% (one-sided type I error = 0.0897).
- C. If the true local recurrence rate is 2.5%, then with 35 patients the probability of observing recurrence of 3.1% or less (≤ 1 out of 35) is 81.0% (Power).
- D. This is as close as we can get to a one-sided equivalence test with 10% type I error and 80% power with exact binomial calculations. The probability of falsely rejecting the null hypothesis (*hypofractionation treatment is worse than standard*) with only 0 or 1 recurrence out of 35 patients is less than 10% if the actual recurrence rate is 12% or more. There will be at least 80% power to reject this hypothesis if the true recurrence is 2.5% or less.

XIV. Considerations for Toxicity, QOL, Disease-Free Survival and Overall Survival (Secondary Endpoints)

- A. Overall survival and disease-free survival will be estimated using the product limit estimator and presented as Kaplan-Meier plots. Cumulative incidence rates will be calculated for local recurrence and adverse events. Quality of life data will be summarized for each time point, and compared using non-parametric statistical methods.
- B. Toxicity will be measured via the CTCAE v. 4.0 and the MSTS score. We will compare toxicity to the standard historical control for preoperative radiation therapy in STS (NCIC, O'Sullivan et. al) (5)
- C. Quality of Life will be measured with the FACT-L validated questionnaire.

XV. References

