APPENDIX III

CTCAE 4.0 Toxicity Grading

Edema

Grade	Toxicity
1	5 - 10% inter-limb discrepancy in volume or circumference at point of greatest visible difference; swelling or obscuration of anatomic architecture on close inspection
2	>10 - 30% inter-limb discrepancy in volume or circumference at point of greatest visible difference; readily apparent obscuration of anatomic architecture; obliteration of skin folds; readily apparent deviation from normal anatomic contour; limiting instrumental ADL
3	>30% inter-limb discrepancy in volume; gross deviation from normal anatomic contour; limiting self care ADL
4	-
5	-

Definition: A disorder characterized by swelling due to excessive fluid accumulation in the upper or lower extremities.

Radiation Dermatitis

Grade	Toxicity
1	Faint erythema or dry desquamation
2	Moderate to brisk erythema; patchy moist desquamation, mostly confined to skin folds and creases; moderate edema
3	Moist desquamation in areas other than skin folds and creases; bleeding induced by minor trauma or abrasion
4	Life-threatening consequences; skin necrosis or ulceration of full thickness dermis; spontaneous bleeding from involved site; skin graft indicated
5	Death

Fibrosis

Grade	Toxicity
1	Mild induration, able to move skin parallel to plane (sliding) and perpendicular to skin (pinching up)
2	Moderate induration, able to slide skin, unable to pinch skin; limiting instrumental ADL
3	Severe induration; unable to slide or pinch skin; limiting joint or orifice movement (e.g. mouth, anus); limiting self care ADL
4	Generalized; associated with signs or symptoms of impaired breathing or feeding
5	Death

Post-operative Wound Complications

Grade	Toxicity
1	Incisional separation of <=25% of wound, no deeper than superficial fascia
2	Incisional separation >25% of wound; local care indicated
3	Hernia without evidence of strangulation; fascial disruption/dehiscence; primary wound closure or revision by operative intervention indicated
4	Hernia with evidence of strangulation; major reconstruction flap, grafting, resection, or amputation indicated
5	Death

Musculoskeletal Tumor Rating Scale-Upper Extremity

PAIN		FUNCTION	EMOTIONAL	HAND POSITIONING	MANUAL DEXTERITY	LIFTING ABILITY
5	No pain	No restriction	Enthused	Unlimited	Unlimited	Normal load
4	Intermediate	Intermediate	Intermediate	Intermediate	Intermediate	Intermediate
3	Modest/Non-disabling	Recreational restriction	Satisfied	Not above shoulder or no/Prosupination	Loss of fine movements	Limited

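### The planned wound-toxicity comparison with the historical trial is not shown to use one definition, so an apparent difference could come from definition alone; its size and direction are unknown

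*Combined protocol and SAP*

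**What the plan says.** **The comparison.** Section XIV.B: "Toxicity will be measured via the CTCAE v. 4.0 and the MSTS score". It continues: "We will compare toxicity to the standard historical control for preoperative radiation therapy in STS", citing the Canadian randomised trial of preoperative versus postoperative radiation. It states no rate, definition, time window, test or margin.

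**The comparator's wound rate.** The Introduction (II) says of that trial that "the major acute wound complication rate was 35% versus 17% in patients who received post-operative radiation therapy". Later in the same section: "The NCI of Canada SR2 trial had a wound complication rate of 43" per cent. Section IX.A.iii, citing the same trial, sets a stopping boundary that "yields the probability of crossing the boundary at most 5% when the complications rate is equal to 50" per cent. None of these places defines the event counted.

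**This trial's wound measure.** The postoperative wound table in Appendix III runs as follows:
- Grades 1 and 2 are incisional separation. Grade 2 is separation of more than a quarter of the wound, with local care.
- Grade 3 is hernia without strangulation, or "fascial disruption/dehiscence; primary wound closure or revision by operative intervention indicated".
- Grade 4 is strangulated hernia, major flap, graft, resection or amputation. Grade 5 is death.

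Section VI.H.iv collects adverse events of grade 3, 4 or 5 and not those of grade 1 or 2. Section VI.H.i does not grade flaps placed at resection or within one month of it, on the ground that they close the primary wound. A flap needed for a wound complication after final closure counts as grade 4.

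**The expectation.** Section VI.H.ii: "Wound complications are expected to develop in about 30-40% of patients", with no grade attached.

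**The concern.** The hypothesis in section III is that local control and toxicity will be similar to conventional fractionation. The Introduction names acute wound complications as a disadvantage of giving radiation before surgery. A reader of the final report will therefore look first at how the wound rate compares with the Canadian trial.

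That comparison sets a rate built from CTCAE grade 3-5 events, with a flap exclusion, beside a published rate whose content the documents never describe. Nothing requires this trial's events to be classified by the comparator's criteria or counted over its time window. If the two definitions differ, the comparison mixes a definition effect with any effect of the schedule.

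The collection rule makes this hard to repair later. A wound more than 25% separated and managed with local care is grade 2 and is not recorded as an adverse event. If the comparator counted such wounds, its rate could not be rebuilt from this trial's adverse event data.

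**Working it through.** **1. The plan's own figure.** XIV.B contains nothing to reproduce. The only computed figure tied to a wound rate is the boundary in IX.A.iii-iv. An exact sequential binomial calculation over patients 1 to 35, halting when the count reaches a listed X by patient N (6/6, 7/7, up to 25/35), gives a crossing probability of 4.99% at a true rate of 50%. The stated limit of 5% is met. The boundary arithmetic is sound; the question is what is counted.

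**2. The two definitions side by side.**

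| Element | This trial | Comparator, as described in the documents |
|---|---|---|
| Event | CTCAE grade 3-5; terms forming the wound rate not listed | major acute wound complication, undefined |
| Open wound under local care (grade 2) | not collected | not stated |
| Flap within one month of resection | not graded | not stated |
| Time window | adverse events up to 2 years, death or new therapy | acute; length not stated |
| Rate | expected 30-40%, grade not stated | 35%, 43%; cited for 50% |

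No row can be matched from the documents.

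**3. The benchmark alone.** Moving from 35% to 43% shifts the target by 8 points, or 0.08 × 35 = 2.8 patients.

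**4. Illustration of a definition effect.** Inputs: n = 35 (X.A); benchmark p0 = 35% (II); no true difference. Let c be the assumed share of comparator-type events that would also count here; the documents do not give it. The expected observed rate is c × 35%. XIV.B has no test, so I use a one-sided exact 5% rule for reading a result as lower. P(X ≤ 7 | 35, 0.35) = 4.2% and P(X ≤ 8 | 35, 0.35) = 8.9%, so the rule is at most 7 of 35. The false-lower probability is P(X ≤ 7 | 35, 0.35c).

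| c | Expected rate | Expected events | P(at most 7 of 35) |
|---|---|---|---|
| 1.0 | 35.0% | 12.2 | 4.2% |
| 0.9 | 31.5% | 11.0 | 9.7% |
| 0.8 | 28.0% | 9.8 | 19.5% |
| 0.7 | 24.5% | 8.6 | 34.7% |
| 0.6 | 21.0% | 7.3 | 54.1% |
| 0.5 | 17.5% | 6.1 | 73.9% |

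Against 43% the same rule becomes at most 9 of 35, with probabilities of 2.7%, 18.4% and 58.4% at c = 1, 0.8 and 0.6. If this trial's criteria counted more than the comparator's, the ratio would exceed 1 and the error would run the other way.

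**5. Sampling error, separately.** An observed 12 of 35 (34.3%) has an exact 95% interval of 19.1% to 52.2%, which contains 35%, 43% and 50%. This says nothing about definition, but it shows how little the comparison can resolve even when definitions match.

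**The case against.** **Direction.** A reader might infer that the plan is biased towards a lower wound rate, because Appendix III has no entry for infection, seroma, haematoma, drainage or readmission. That matters only if the comparator counted them, and the documents do not say so. Grade 3-5 collection and the flap rule make a lower rate plausible, not established. This objection stands.

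**Scope of the scale.** It is also tempting to say that only the events in the Appendix III wound table can count. That is too strong. VII.F applies CTCAE v4.0 as a whole and VI.H.iv collects all grade 3-5 events, so a grade 3 wound infection can be recorded. The gap is narrower: the plan does not say which terms make up the wound rate.

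**Safety monitoring.** A reader might conclude that the halting rule misses events for the same reason. The documents do not support this. The IX.A.iii boundary is calibrated at 50%, IX.A.iv words its counts as treatment-related grade 3-4 adverse events, and X.B.ii closes the study at 60% or more with postoperative wound complications and no grade limit. These need reconciling, but they do not show a shortfall.

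**Size.** The Introduction's figure for the 25 Gy series, "Seven percent of patients needed surgery to address these toxicities", might be taken to show how far an operative definition falls below 35%. It cannot: it comes from another schedule, and the toxicities meant were mostly erythema and desquamation.

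**Importance.** The comparison is secondary in a single-arm pilot, and XIV.B says toxicity without naming wounds or a test. This limits the consequence to interpretation but does not make the rates comparable.

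**Conclusion.** The point holds in this form: the wound rate this trial will produce is not shown to be comparable with the historical rate, and an apparent difference can come from definition alone. Three features of the text support it: the comparator outcome is undefined, collection here starts at grade 3 with early flaps ungraded, and the historical rate is not a single figure.

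The size cannot be fixed from the documents. Under the stated assumptions (35 patients, no true difference, 35% benchmark, illustrative one-sided 5% rule), the chance of wrongly reading the rate as lower rises from 4.2% with full capture to 19.5% at 80% and 54.1% at 60%. The capture shares are assumptions, and the direction itself is unproven. The primary endpoint is unaffected. The change should be made before the toxicity comparison is reported, and ideally while wound events can still be recorded prospectively.

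**What to change.** In XIV.B:
- State the comparator's published wound definition and time window.
- Classify every postoperative wound event on that definition as well as by CTCAE.
- Record wound events of any grade for this purpose, as an exception to VI.H.iv.
- State how flaps are handled on both sides.
- Make the historical wound comparison only on this variable, as a descriptive estimate with an exact 95% interval, against one benchmark after reconciling 35%, 43% and 50%.

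Keep CTCAE grading for monitoring and add no new terms to the IX.A.iii halting count, since its 50% reference was not set for them. Instead, reconcile which wound events IX.A.iii, IX.A.iv and X.B.ii count. The institutional database in XI.D already holds wound complications and might be rescored on the same definition if its records allow.

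Cost: some extra abstraction for up to 35 patients, who already have a wound visit after surgery (VII.B), plus wording changes. The reported complication rate may be higher than under CTCAE grade 3-5 alone.
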